## 5.7 Adherence/Compliance

- We plan to enroll 40 evaluable participants. Adjusting for the 5% non-evaluable sample rate and 10% attrition rate, our goal is to randomize a total of 48 participants to yield at least 40 evaluable participants.
- Compliance is defined as 100% adherence to the vaccination schedule.
- For the primary endpoint of change in the number of nelipepimut-S-CTL for an individual participants between the pre-vaccination timepoint and the 1 month (+/- 7 days) after surgery timepoint, “evaluable” will be defined as completing all pre-surgical vaccinations and the visit at 1 month (+/- 7 days) after surgery.
- For the safety endpoint, participants who receive at least one vaccination will be included in the safety evaluation.
- For all secondary endpoints, all non-compliant participants will be analyzed according to the intent-to-treat principle. All levels of compliance will be included in the full evaluation of endpoints if paired biopsies are available.

## 6. PHARMACEUTICAL INFORMATION

### 6.1 Study Agent (IND # [REDACTED], IND Sponsor NCI DCP)

#### *Physical description of agents:*

NeuVax™ appearance: Clear, colorless solution, essentially free from visible particulates;

GM-CSF (Leukine®, sargramostim) appearance: The liquid Leukine presentation is formulated as a sterile, preserved, injectable solution in a vial. Lyophilized Leukine is a sterile, white, preservative-free powder that requires reconstitution with 1 mL Sterile Water for Injection.

#### *Formulation to be used in this study and excipients:*

The vaccine NeuVax™, also known as nelipepimut-S, is a nine amino acid peptide (KIFGSLAFL) derived from the HER2 protein that is overexpressed in many breast cancer patients (reviewed in [16]). Vaccines containing the nelipepimut-S peptide mixed with an immunoadjuvant have proven to be efficacious in early phase (phase I/II clinical trials) conducted in the adjuvant setting to prevent recurrence of breast cancer [11].

The NeuVax vaccine (nelipepimut-S; as 1.5 mg/mL nelipepimut-S acetate solution) will be supplied by SELLAS. GM-CSF (as 250 µg lyophilized Leukine) will be supplied by NCI Repository, MRI Global.

GM-CSF is a potent cytokine. Recombinant human GM-CSF is a 14.6 kDa globular protein consisting of 128 amino acids containing 2 intramolecular disulfide bonds and 2 potential N-linked glycosylation sites. Known adverse effects of GM-CSF include bone pain, allergic reactions, lethargy, malaise, anorexia, skin rashes, flushing, fever, and chills. At doses higher than planned in this study, weight gain may be seen along with breathing difficulties, blood clots, and collections of fluid around the heart or lungs, dyspnea, thromboembolic phenomena, and pleural and pericardial effusion.

Leukine® (sargramostim) is a recombinant human granulocyte-macrophage colony stimulating factor (rhu GM-CSF) produced by recombinant DNA technology in a yeast (*S. cerevisiae*) expression system. Biological potency is expressed in International Units (IU) as tested against the World Health Organization (WHO) First International Reference Standard. The specific activity of GM-CSF is approximately  $1.4 \times 10^6$  IU/mL. See GM-CSF (Leukine® (sargramostim)) package insert and labeling for additional details.

The nelipepimut-S vaccine acetate drug substance is a 9-amino acid peptide produced by solid-phase peptide synthesis. Nelipepimut-S acetate drug product is manufactured by Oso Biopharmaceuticals Manufacturing, LLC, Albuquerque, NM as a 1.5 mg/mL solution in 1 mL sterile water for injection (SWFI) in a 2-mL glass vial. Each mg of nelipepimut-S acetate is equivalent to 0.94 mg of nelipepimut S peptide. Hence, the vaccine concentration is equivalent to 1.42 mg/mL nelipepimut-S peptide. The control is SWFI.

Prior to administration, 1,136 µg (0.8 mL) of the nelipepimut-S acetate or control is mixed by the pharmacist or pharmacy technician under the supervision of the pharmacist with 1 mL of reconstituted lyophilized Leukine® GM-CSF (reconstituted as 250 µg/mL in solution). Immediately after mixing, the study drug is withdrawn into four 1 mL syringes and within 2 hours of mixing, a total of 1.6 mL is administered as 4 intradermal injections to deliver a total of 1,000 µg of nelipepimut-S peptide vaccine (1,010 µg of nelipepimut-S peptide). The control vial contains 1 mL SWFI. The detailed guidance for mixing nelipepimut-S (or control) solution from lyophilized Leukine® 250 µg and test drug (nelipepimut-S solution or control) is stated in **Appendix B**.

## 6.2 Reported Adverse Events and Potential Risks

Phase I trials addressing the immunogenicity and toxicity of escalating nelipepimut-S peptide doses mixed with GM-CSF as adjuvant were conducted in patients with metastatic breast and ovarian cancer. Of the 14 subjects enrolled, a majority experienced mild pain at the injection site. Low-grade fever, nausea, fatigue, myalgia, itching at the injection site, and back and abdominal pain were also noted. One subject reported grade 2 chills, headache and ulceration at the injection site. No grade 3 AEs were reported. The side effects observed were not dose-dependent.

Two concurrent Phase II trials in both node-positive and node-negative breast cancer patients disease-free after standard treatment were recently completed [13, 27] (CCRE08140797). These trials were designed to address the ability of the vaccine to prevent disease recurrence. Subjects were observed for an hour after injection for any signs of hypersensitivity, and asked to return 48–72 hours later to monitor local/systemic reactions to injection. In a total of 187 subjects, local reactions included grade 1 erythema and induration, pain and soreness at the injection site (81% of vaccinated subjects) and grade 2 pruritus (19%). Systemic reactions included grade 1 headache and fatigue (71%); grade 2 pain, flu like symptoms, and fatigue (14%); and grade 3 angioedema of tongue and bone pain (2%). No grade 4 or 5 events were observed. Because the inoculations are very well tolerated with few immediate adverse events, only post inoculation vital signs will be assessed at 30 +/- 5 minutes after inoculation by the research nurse or coordinator.

The same vaccine (nelipepimut-S+GM-CSF) was evaluated in prostate cancer patients expressing varying levels of HER2/*neu* protein [25]. Of the 40 enrolled subjects, grade 1 local reactions were observed in all; systemic reactions were observed in 38.1% (grade 1) and 9.5% (grade 2).

These effects are likely attributable to GM-CSF. In studies utilizing this adjuvant, patients sometimes complained of mild to moderate flu-like symptoms (fever, chills, achiness, and fatigue) for 1–2 days after vaccination. In subsequent studies evaluating the AE37 vaccine (AE37 + GM-CSF), the toxicity profile was similar in patients randomized to receive the vaccine and those randomized to receive GM-CSF only (unpublished data).

Nelipepimut-S was recently evaluated in a multicenter, multinational, prospective, randomized, double-blind, controlled phase III study (NCT01479244; PI: [name]) The trial randomized 758 lymph node-positive breast cancer patients with HER2 1+/2+ tumors in the adjuvant setting. Randomization was completed in April 2015. In June 2016, the Independent Data Monitoring Committee (IDMC) met to complete a planned safety and futility interim analysis that was triggered after 70 qualifying DFS events were reached. At that time, the IDMC recommended that the trial be stopped due to futility. The AEs observed in the Phase III study as of the date of the last data cutoff (16 Jan 2015) were consistent with the reactions observed in previous studies. AEs reported for  $\geq 10\%$  of patients in the pivotal study have been limited to local injection site reactions, including induration (56%), swelling (46%), pain (40%), pruritus (55%), and edema (17%). AEs reported for  $<20\%$  of patients have included headache, fatigue, back pain and nausea. AEs have been generally mild in severity, with no safety trends identified for Grade 3 or higher AEs or SAEs/deaths. Two patients in the pivotal phase III study reported AEs related to study drug hypersensitivity including 1 patient with non-serious, Grade 2 angioedema and 1 patient with a Grade 4 SAE of anaphylactic reaction, both of which were considered definitely related to study drug, resulted in discontinuation of treatment, and were noted to have resolved. In addition, one patient in the early phase trials reported Grade 3 angioedema assessed as related to rhGM-CSF. No other allergic- or anaphylactic-type reactions to E75 plus the rhGM-CSF adjuvant have been reported.

### 6.3 Availability

NeuVax™ is provided to the NCI under a Clinical Trials Agreement (CTA) between SELLAS and the DCP, NCI (see §12.7).

### 6.4 Agent Distribution

Agents will only be released by NCI, DCP after documentation of IRB approval of the DCP-approved protocol and consent is provided to DCP and the collection of all Essential Documents is complete (see DCP website for description of Essential Documents).

NCI, DCP-supplied agents may be requested by the Investigator (or their authorized designees) at each Organization. DCP guidelines require that the agent be shipped directly to the institution or site where the agent will be prepared and administered. DCP does not permit the transfer of agents between institutions (unless prior approval from DCP is obtained). DCP does not automatically ship agents; the site must make a request. Agents are requested by completing the DCP Clinical Drug Request form (NIH-986) (to include complete shipping contact information) and faxing or mailing the form to the DCP agent repository contractor:

[name]  
MRIGlobal  
DCP Repository  
[name]  
[name]  
[contact]  
[contact]  
Emergency [contact]

## 6.5 Agent Accountability

The Investigator, or a responsible party designated by the Investigator, must maintain a careful record of the inventory and disposition of all agents received from DCP using the NCI Drug Accountability Record Form (DARF) or an institutionally-approved accountability system. The Investigator is required to maintain adequate records of receipt, dispensing and final disposition of study agent. Include on receipt record from whom the agent was received and to whom study agent was shipped, date, quantity and batch or lot number. On dispensing record, note quantities and dates study agent was dispensed and administered to each participant. Drs. [name] or [name], [name] and [name] or their representatives will be responsible for study agent accountability for participants at Dana-Farber Cancer Center, UT MD Anderson Cancer Center, and Thomas Jefferson University, respectively.

## 6.6 Packaging and Labeling

NeuVax™ will be provided by SELLAS and will be distributed to the clinical sites by MRI Global. GM-CSF (as 250 µg lyophilized Leukine) will be supplied to the clinical sites by NCI Repository, MRI Global.

## 6.7 Storage

For detailed storage instructions of the components of the vaccine (nelipepimut-S acetate and GM-CSF) please follow the instructions in the Investigator's Brochure. The components of the active study drug and the control will be stored separately in the research pharmacy and reconstituted when needed. The components will be stored as per appropriate storage temperature designated on clinical carton label. All study drug components (nelipepimut-S acetate and GM-CSF) will be stored under refrigerated conditions ( $5^{\circ}\text{C} \pm 3^{\circ}\text{C}$ ).

## 6.8 Registration/Randomization

### *Screening and Registration into the DMI Database:*

Once informed consent has been signed, participants will be registered into the DMI database. The DMI database will assign a participant's PID upon completion of the registration process.

### *Randomization:*

Participants will be assigned a randomization number once the following has been accomplished: eligibility has been verified at the site level, eligibility has been confirmed by the site PI, and eligibility CRF has been entered into the DMI web application. The randomization number will be generated by the database and assigned to the participant. Refer to **Section 13.2** for details of randomization.

*Screening/Registration/Randomization into site-specific databases:*

The DMI is the database of record for the study. Registration and randomization should occur per the procedures outlined above. If the site staff need to enter study data into site-specific electronic databases per their institutional requirements, they should do so in accordance with their institutional policies and procedures.

Appropriate CRFs must be completed for any participant who signs an informed consent. If a consented participant is a screen failure and deemed ineligible, the following CRFs must be completed: 1) the Registration CRF; 2) the Randomization CRF with the eligibility box checked “no”, 3) the Inclusion and Exclusion CRFs showing why the participant is ineligible, 4) the Off-Study CRF, 5) the Adverse Event CRF, 6) the Concomitant Medication CRF and 7) the Verification CRF. If no Adverse Event and/or Concomitant Medications were assessed by the time the participant is deemed ineligible, the “NONE” box will be checked to complete both CRFs. All participants who sign an informed consent must formally go off study. All participant registration information will be entered into DMI. If a participant experiences a serious Adverse Event during the screening process, a Serious Adverse Event (SAE) form must be completed.

## **6.9 Blinding and Unblinding Methods**

- 6.9.1 Participants will be blinded to NeuVax™ or GM-CSF alone arm assignment.
- 6.9.2 The Statistician, Site Study Pharmacist and other investigators will not be blinded to NeuVax™ or GM-CSF alone arm assignment.
- 6.9.3 Participants randomized to the nelipepimut-S/GM-CSF arm will receive two vaccinations of nelipepimut-S (1000 µg) and GM-CSF (250 µg) consisting of 4 intradermal inoculations two weeks apart prior to surgery. Participants randomized to the GM-CSF alone arm will receive inoculations of GM-CSF (250 µg) administered in an identical manner to those receiving nelipepimut-S/GM-CSF.
- 6.9.4 At the end of the study participants will be unblinded to their assignment.
- 6.9.5 Study agents may be unblinded during the course of the study if deemed medically necessary in the event of a serious adverse event after discussion with the NCI medical monitor. Unblinding will be conducted as follows:
  - 1) The Site PI contacts the Protocol Principal Investigator ([name], PhD) and requests the participant’s treatment status be unblinded.
  - 2) The Protocol Principal Investigator ([name], PhD) contacts the NCI DCP Medical Monitor ([name], MD) and requests the participant’s treatment status be unblinded. The Protocol Principal Investigator then conveys the Medical Monitor’s decision to the Site PI. The Site PI then proceeds with unblinding as written out below.
  - 3) If the NCI Medical Monitor cannot be reached and the participant requires emergency care, the Protocol Principal Investigator ([name]) may authorize the site PI to break the blind.
  - 4) If the Site PI is unable to reach the Protocol Principal Investigator and the participant requires emergency care, then the Site PI must proceed with unblinding as written out below.
  - 5) The Site PI officially unblinds the participant and takes the participant off-study.
  - 6) The date and reason for breaking the blind must be submitted by the Site PI to the Protocol Principal Investigator, [name], PhD as soon as possible.

- 7) It is the responsibility of the Protocol Principal Investigator to report the date and reason for breaking the blind to the NCI Medical Monitor, [name], MD as soon as possible after receiving this information from the Site PI.

NCI Medical Monitor:  
[name], MD  
NCI/Division of Cancer Prevention  
[name]  
[name]  
[name]  

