### **5.6 Dose Modification**

In our previous trials evaluating Nelipepimut-S + GM-CSF, approximately 18% of patients experienced robust local reactions ( $>100\text{mm}$ ) or greater than or equal to grade 3 local or systemic reactions or greater than or equal to grade 2 hypersensitivity reactions [26]. For a description of how local reaction will be

measured, refer to section 7.3.1. To avoid higher grade toxicities, for participants meeting any of these criteria, we will dose-reduce the GM-CSF component of the vaccine as outlined below. Site PIs cannot make the decision to dose-reduce without consulting with [name]. The decision to dose-reduce the GM-CSF will be made by the Protocol Principal Investigator, [name], who will communicate the need for dose-reduction to the individual site PI and site study research nurse / or coordinator who will be generating the orders for the pharmacy for preparation of vaccine. Adverse events that do not respond to either dose modification or clinical management of the reaction will result in taking the participant off agent but followed for study endpoints (refer to Section 8.3: Off-Agent Criteria).

Inoculations will be immediately halted if any serious adverse reactions occur to include: death, life-threatening adverse drug experience (i.e., severe anaphylactic reaction immediately after vaccine administration), inpatient hospitalization or prolongation of existing hospitalization, a persistent or significant disability/incapacity, a congenital anomaly/birth defect, or other important medical events that may not result in death, be life-threatening, or require hospitalization but which, when based upon appropriate judgment of the PI, be determined to jeopardize the participant or require medical or surgical intervention to prevent an outcome listed above.

Participants experiencing Grade 4 toxicities of any attribution will be taken off agent and followed (refer to Section 8.3: Off-Agent Criteria). Any participant with Grade 3 systemic toxicities possibly, probably or definitely attributable to study drug will be taken off agent and followed, except for participants with skin toxicities. Any participant experiencing Grade 3 skin toxicities will continue to receive inoculations as long as their skin toxicity has resolved prior to the next scheduled inoculation. Participants with Grade 3 toxicities not related or unlikely related to study agent will continue on study.

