### 11.1.4 Assessment of relationship of AE to treatment

The possibility that the adverse event is related to study agent will be classified as one of the following: not related, unlikely, possible, probable, definite.

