## **13. STATISTICAL CONSIDERATIONS**

### **13.1 Study Design/Description**

This is a Phase II, randomized, single-blind study with 2 intervention arms. A total of 108 DCIS participants will be consented and screened for eligibility and, with a conservative estimate, 48 (45%) participants are expected to be HLA-A2 positive. These 48 participants will be randomized 2:1 to vaccine and GM-CSF alone groups. Accounting for 10% attrition rate while on study and for approx. 5% non-evaluable sample rate, we expect to have 40 evaluable participants, 27 in vaccine and 13 in GM-CSF alone group, that have all baseline, post-vaccination (pre-surgery), and post-surgery measures of nelipepimut-S-specific CTL. With 27 and 13 in vaccine and GM-CSF alone groups, respectively, we will have 82% power to detect an effect size of 1 on the change of nelipepimut-S-specific CTL ("1 month (+/- 7 days) after completion of the vaccination series timepoint" minus pre-1st vaccine) between the two groups, corresponding to change of  $0.05\% \pm 0.05\%$  in vaccine group and  $0 \pm 0.05\%$  in control group, using two-sided t-test with a significance level of 0.05.

The decision rule for declaring the agent promising will be if we detect an effect size of 1 on the change of nelipepimut-S-specific CTL, and if there are not greater than 10% grade III AEs attributed to the active

study drug or IV AEs of any attribution. Completion of the current study will provide the necessary data to determine the next phase of study, specifically whether a subsequent, larger phase II will be conducted versus a phase III study.

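### Section 6.9 leaves investigators unblinded to arm without need and conflicts with its own unblinding procedure, so the grade III part of the promising rule can rest on attribution by staff who know the arm.

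*Combined protocol and SAP*

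**What the plan says.** Section 13.1 declares the design: "This is a Phase II, randomized, single-blind study with 2 intervention arms". Section 6.9.1 blinds the participants. Section 6.9.2 then says: "The Statistician, Site Study Pharmacist and other investigators will not be blinded". No reason is given that would apply to anyone beyond the pharmacist, who has to prepare the dose.

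Section 6.9.5 describes how the blind is broken after a serious event. The Site PI asks the Protocol PI, who asks the medical monitor. If the monitor cannot be reached in an emergency, the Protocol PI "may authorize the site PI to break the blind". The Site PI then unblinds the participant and takes her off study.

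The promising rule in 13.1 has a CTL condition and a safety condition. The safety condition is met "if there are not greater than 10% grade III AEs attributed to the active" "study drug or IV AEs of any attribution". On attribution, 11.1.4 says: "The possibility that the adverse event is related to study agent will be classified as one of the following", followed by five levels from not related to definite. It does not name who classifies.

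Sections 8.2.1 and 13.5 compare toxicity between arms as a secondary objective. Section 10.2 gives specimens blinded IDs and blinds the receiving laboratories to participant information and visit. It does not mention arm.

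**The concern.** Attribution is a judgement, and the plan allows the person making it to know the arm. Section 5.6 also states a prior view, that the vaccine's toxicity comes from GM-CSF. An assessor who holds that view and knows the arm has room to call a vaccine-arm event unrelated to the active drug, and knows that a control-arm event cannot be due to the peptide. An assessor could equally lean towards over-attribution in the vaccine arm.

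Three things depend on these judgements: the grade III part of the promising rule, the tabulation of events by relationship (13.5), and removal from agent under 5.6 ("Any participant with Grade 3 systemic toxicities possibly, probably or definitely attributable to study drug will be taken off agent and followed"). Grading, which feeds the between-arm comparison, is also open to influence when the arm is known.

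The exposure looks avoidable because the arms are already matched in the pharmacy. Section 6.9 also leaves a site unable to tell whether its PI is meant to be blinded.

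**Working it through.** **1. Is the unblinding needed?**

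| Element | Vaccine | GM-CSF alone | Source |
|---|---|---|---|
| Prepared by | Pharmacist or supervised technician | Same | 6.1 |
| Added to 1 mL reconstituted Leukine | 0.8 mL peptide solution, clear and colourless | 0.8 mL sterile water | 6.1, Appendix B |
| Given | Four 0.4 mL injections, 1.6 mL | Same | 5.2, Appendix B |
| Reduced GM-CSF preparation | Provided | Provided | Appendix B |

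Nothing here requires anyone outside the pharmacy to know the arm. An order for a reduced dose need not disclose it either, since both arms have that preparation.

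**2. Do 6.9.2 and 6.9.5 agree?** Under 6.9.2, investigators know the arm. Under 6.9.5, the Site PI must ask for treatment status, wait for a decision and then break the blind. If the Site PI is an unblinded investigator, the request has little function. If the Site PI is blinded, 6.9.2 is wrong as worded.

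**3. The plan's own figure.** The only related stated figure is 82% power with 27 and 13 evaluable, effect size 1 and a two-sided 0.05 t-test (13.1). The noncentrality is 1/√(1/27 + 1/13) = 2.96 on 38 degrees of freedom, which gives power 0.823. The figure reproduces, and blinding assessors does not change it.

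**4. How sensitive is the 10% limit?** The rule names no denominator and does not say which of the five levels count as attributed. Counting participants, with no grade IV events, and taking 48 × 2/3 = 32 randomised to vaccine:

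- 3/32 = 9.4%, pass
- 4/32 = 12.5%, fail

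Under other denominators the boundary is 2/27 (7.4%) against 3/27 (11.1%), or 4/48 (8.3%) against 5/48 (10.4%). In each case one participant separates pass from fail.

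**5. How often would that matter?** For true rate p and share s of related events that are attributed to drug:

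P(fail) = P(X ≥ 4), X ~ Binomial(32, p·s) = 1 − Σₖ₌₀³ C(32,k)(ps)ᵏ(1−ps)³²⁻ᵏ

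| True rate p (assumed) | s = 1 | s = 0.75 (assumed) |
|---|---|---|
| 2% | 0.004 | 0.001 |
| 5% | 0.07 | 0.03 |
| 10% | 0.40 | 0.22 |
| 15% | 0.73 | 0.49 |

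At 15%, the same shift moves P(fail) from 0.79 to 0.60 with n = 27 and from 0.87 to 0.64 with n = 48. For scale, 2.3 reports grade 3 systemic toxicity in 2% of earlier vaccinated participants, with local reactions of grade 1 or 2 only. The 18% in 5.6 is a composite that includes reactions over 100 mm and grade 2 hypersensitivity, so it is not a grade III rate.

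**The case against.** Single-blind is a declared choice, and the primary endpoint is a flow-cytometry count. That stands as far as it goes, but the label does not explain why AE assessors should know the arm, and the safety condition is not a laboratory count.

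Section 6.9.5 can be read as governing only the breaking of the participant's own blind. That is possible, but the steps in which the Site PI requests treatment status fit it poorly. If the Site PI is in fact blinded and does the attribution, the bias concern shrinks and a wording error in 6.9.2 remains.

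A reader might infer more than the documents support:

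- **That the whole safety condition depends on attribution.** The grade IV part counts events whatever their cause. Section 11.1.1 records events before surgery whether or not related, so an all-cause comparison is available, although grading could still be influenced.
- **That unblinded site investigators decide GM-CSF reductions.** Section 5.6 reserves that decision to the Protocol PI.
- **That the CTL result is equally exposed.** Section 10.2 already blinds laboratories to participant information and visit. The gap is that arm is not named.
- **That the go decision is likely to be distorted, as a fall in P(fail) from 0.73 to 0.49 suggests.** That needs a 15% rate, far above the 2% in 2.3, together with an assumed denominator, an assumed one-quarter shift and an assumed direction.

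**Conclusion.** The concern holds as a design weakness together with an internal inconsistency. Sections 6.9.2 and 6.9.5 must be reconciled. As written, grade III attribution and AE grading can be done by staff who know the arm, with no blinded adjudication and no stated need. That these staff do the attributing is inferred, because 11.1.4 names nobody.

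The size is illustrative. One participant can reverse the verdict at the 10% boundary under any of the three denominators considered. With 32 as the denominator, the chance of reaching the failing side is 0.73 at an assumed 15% rate and 0.004 at 2%. The documents give no basis for the direction or size of any bias, so this point does not show that the safety conclusion will be wrong. It shows that the conclusion is less protected than it could cheaply be.

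**What to change.** - In 6.9.2, limit the unblinded roles to the site pharmacist and the statistician/database staff.
- In 11.1.4, name who grades and attributes AEs (Site PI, research nurse or coordinator) and state that they stay blinded to arm. They would attribute to the study agent as given, and the statistician would apply the 13.1 rule by arm afterwards.
- In 13.1, state the denominator of the 10% limit and which attribution levels count.
- In 10.2, add arm to the items withheld from laboratories, and name the study pathologist.
- Reconcile the 6.9.5 step that takes an unblinded participant off study with 8.3, which keeps following off-agent participants for endpoint data where possible.

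**Cost.** There is no change to the 48 randomised or to the 82% power, and no new staff. Pharmacy orders, which 5.6 has the site nurse or coordinator generate, must be arm-neutral, and so must the database views. The 6.9.5 route would sometimes be used. While its off-study step stands, each use could lose endpoint follow-up, which matters with only 13 evaluable controls planned.

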### 8.3 Off-Agent Criteria

Participants may stop taking study agent for the following reasons: completed the protocol-prescribed intervention, adverse event or serious adverse event, inadequate agent supply, noncompliance, concomitant medications, medical contraindication, or pregnancy. Participants will continue to be followed, if possible, for safety reasons and in order to collect endpoint data according to the schedule of events.

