### 8.4 Off-Study Criteria

Participants may go ‘off-study’ for the following reasons: the protocol intervention is completed, AEs, SAEs, lost to follow-up, participant’s refusal of follow up, participant withdrawal (*e.g.*, due to toxicity unacceptable to the participant or the investigator), physician decision to take the participant off study, other reason (*e.g.*, determination of ineligibility including screen failure, non-compliance, pregnancy or medical contraindication), abnormal results of ECHO at baseline (defined as an ejection fraction less than the institution’s lower limit of normal), or death. Participants found to be ineligible during the screening phase and after signing the Informed Consent document and assigning the PID number, will be considered “screen failures”. Such participants will be taken off study and the appropriate end of study CRFs will be completed for these participants. In cases of early termination, when possible, participants

will be asked to return to the clinic site prior to going off study for an early termination visit according to the Schedule of Events.

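### Emergency unblinding takes a woman off study, while 5.6 and 8.3 keep women with the same events in follow-up; 8.4 blurs the line further, so later scheduled data can go missing for outcome-related reasons

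*Combined protocol and SAP*

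**What the plan says.** Section 6.9.5 of the combined protocol and SAP limits mid-study unblinding to one situation: "Study agents may be unblinded during the course of the study if deemed medically necessary in the event of a serious adverse event". The decision is discretionary and is discussed with the medical monitor, unless an emergency prevents this. Once it is taken, step 5 is not discretionary: "The Site PI officially unblinds the participant and takes the participant off-study".

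Section 5.6 treats severe toxicity differently: "Participants experiencing Grade 4 toxicities of any attribution will be taken off agent and followed". The same section takes a woman off agent, but still follows her for study endpoints, if urticaria leads to intravenous steroids or hospitalization.

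Section 8.3 lists completed intervention as an off-agent reason, along with "adverse event or serious adverse event, inadequate agent supply, noncompliance, concomitant medications, medical contraindication, or pregnancy". It then says: "Participants will continue to be followed, if possible, for safety reasons and in order to collect endpoint data according to the schedule of events".

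Section 8.4 opens with "Participants may go ‘off-study’ for the following reasons". Its list includes "the protocol intervention is completed, AEs, SAEs, lost to follow-up" and, further on, "non-compliance, pregnancy or medical contraindication". It asks for an early termination visit when possible.

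For pregnancy, 5.2 discontinues the participant from the study, and 7.2, 7.3.1 and 7.3.2 require off-study status with the pregnancy followed to term. Section 8.3 lists pregnancy as an off-agent reason with continued follow-up.

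**The concern.** A woman hospitalized for a reaction meets the serious-event definition in 11.2.1. If she is unblinded, 6.9.5 ends her participation, while 5.6 and 8.3 keep her on the schedule. Sites could handle identical cases differently and each be following the protocol.

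Whether she leaves would depend on what happened to her after vaccination, so the missing data would be related to outcome. Section 13.6 drops a missing primary value and offers no other handling. The decision rule in 13.1 counts grade IV events of any attribution, yet the provisions that could outlast off-study status are tied to attribution. Section 11.2.2.6 follows agent-related serious events to resolution, and the follow-up call in 11.1.5 covers only events attributed possibly, probably or definitely to the agent. Later events, and serious events judged unrelated, are therefore the exposed part.

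**Working it through.** **1. The reasons side by side**

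| Situation | Off agent, follow-up continues | Off study |
|---|---|---|
| Serious event, participant unblinded | 8.3, if possible; 5.6 for grade 4 toxicity and for urticaria needing hospitalization | 6.9.5 step 5, required |
| Adverse or serious event, not unblinded | 8.3; 5.6 | 8.4, permitted |
| Non-compliance | 8.3 | 8.4, permitted |
| Medical contraindication | 8.3 | 8.4, permitted |
| Pregnancy | 8.3 | 5.2, 7.2, 7.3.1, 7.3.2, required; 8.4, permitted |
| Intervention completed | 8.3 | 8.4, permitted |

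No section ranks these rules. Only the unblinding and pregnancy rows set a mandatory off-study rule against continued follow-up.

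**2. What is lost, by time of unblinding**

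Section 7.1 puts injection 2 at Day 14, surgery at Day 28 and the post-vaccination visit 30 days after surgery, so at about Day 28 + 30 = Day 58.

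- *Before injection 2, which is then not given.* She is already non-evaluable under 5.7 and 13.8. Her later CTL values matter only for the evaluable versus non-evaluable comparison in 13.8 and the repeated-measures analysis in 13.4.
- *Between injection 2 and the 1-month visit*, about 58 − 14 = 44 days. This is a true loss from the primary set. An early termination sample may exist, but not at the defined timepoint.
- *After the 1-month visit.* The primary value exists. The final CTL sample and final examination can be lost.

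In the first two cases the 1-month ECHO can also be lost. Section 7.4.1 makes an ejection-fraction fall of more than 10% a reportable serious event.

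**3. Power**

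Inputs from 13.1: 27 and 13 evaluable, effect size 1, two-sided t-test, α = 0.05, stated power 82%.

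Noncentrality = 1/√(1/27 + 1/13) = 1/√0.11396 = 2.962, with 27 + 13 − 2 = 38 degrees of freedom. The noncentral t distribution gives 82.3%, so the plan's figure is reproduced.

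The evaluable number also holds approximately: 48 × 0.90 × 0.95 = 41.0, or 48 × 0.85 = 40.8, against 40 stated.

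The documents give no expected number of unblindings. Assuming up to four losses beyond plan:

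| Vaccine / control | Power |
|---|---|
| 27 / 13 | 82.3% |
| 26 / 13 | 81.8% |
| 25 / 13 | 81.2% |
| 24 / 13 | 80.6% |
| 23 / 13 | 80.0% |
| 27 / 12 | 80.2% |
| 26 / 12 | 79.6% |
| 27 / 11 | 77.7% |

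One vaccine woman costs about 0.5 points (82.3 − 81.8). One control woman costs about 2 points (82.3 − 80.2).

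**The case against.** The protocol has real safeguards. Serious events are reported within 24 and 48 hours (11.2.2), agent-related ones are followed to resolution, and anyone with at least one vaccination stays in the safety evaluation (5.7, 13.8). Section 8.4 is permissive and asks for an early termination visit. Unblinding is rare and discretionary, and 10% attrition is already budgeted. All of this stands, and it limits the point to later scheduled data. It does not resolve the conflict in 6.9.5 step 5, which is mandatory.

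A reader might infer three stronger claims that the documents do not support.

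- *The most serious safety cases are lost.* The triggering event is reported and the woman remains in the safety set. Only what follows is exposed.
- *Every woman may leave before the primary sample, because intervention completion is an off-study reason.* Section 3 keeps each participant on study through the final follow-up visit, for up to 8 months. Sections 7.4 and 7.5 schedule the post-operative visits, and 8.3 treats completed intervention as off-agent. Since 6.8 requires every consented woman to go off study formally, 8.4 reads most naturally as a list of disposition reasons. The wording is loose, no more.
- *The 10% safety rule could turn on one lost woman, for example 3 of 32 against 4 of 32.* Section 13.1 states no denominator; 32 is simply two thirds of 48. The event that led to unblinding has already been counted. Only a later qualifying event could be missed.

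Nor is it clear that non-compliant women are promised intent-to-treat analysis of the primary CTL endpoint. Section 5.7 ties that principle to secondary endpoints, and 13.8 ties it to biomarker endpoints.

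**Conclusion.** The contradiction is in the text and should be corrected. Step 5 of 6.9.5 requires off-study status for a woman unblinded for a serious event, while 5.6 and 8.3 continue follow-up for women with the same kinds of event. Section 8.4 adds to the ambiguity by permitting off-study status for reasons that 8.3 treats as off-agent.

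The practical size is modest. The number of unblindings is not given and is assumed to be small, and the effect on the primary set is confined to the window between injection 2 and the 1-month visit. The power cost is minor unless several control women are lost. What justifies the change is that the missing data would be selected by outcome, would include safety data bearing on the decision rule, and can be avoided.

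The documents give no analytic reason for unblinding to end data collection. Section 6.9.2 already leaves the statistician, the site pharmacist and other investigators unblinded, and 10.2 keeps participant information and visit from the laboratories.

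**What to change.** Reconcile 6.9.5 step 5 and 8.4 with 5.6 and 8.3 by defining two separate statuses: end of study agent and end of data collection. For each listed reason, state whether scheduled safety and endpoint collection continues.

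- Unblinding a participant should not by itself end her data collection. Step 6 of 6.9.5 already records the date and reason, so data collected afterwards can be identified in the analysis.
- Clarify in 8.4 that completion of the intervention does not take a woman off study before the scheduled post-operative visits.
- The sponsor must reconcile the pregnancy passages (5.2, 7.2, 7.3.1 and 7.3.2 against 8.3). No view is offered here on which clinical rule should apply.

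The cost is a wording amendment across these sections, with the approvals that 14.3 requires. It adds no visits, samples or participants and leaves treatment decisions unchanged.
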